## IIIC.4f.2. Measures for Primary Hypothesis Testing

**IIIC.4f.2a. Youth Psychological Protective Processes:** This index consists of seven measures (**Appendix 1**).

**IIIC.4f.2a.1. Resistance Efficacy:** Participants respond to three versions of a scenario to report the actions they believe they would take if presented with the chance to drink alcohol, smoke cigarettes or use marijuana.

**IIIC.4f.2a.2. Self-control:** The 25-item Self-Control Inventory includes items of good self-control (e.g. delay of gratification, planning, problem-solving, dependability, and soothability) and poor self-control (e.g. impulsivity, immediate gratification, distractibility, and low frustration tolerance).

**IIIC.4f.2a.3. Future Orientation:** The Time Perspective Inventory consists of the future, present/hedonistic, and present/fatalistic subscales. The future subscale reflects formulation of goals and plans to achieve them.

**IIIC.4f.2a.4. Emotion Regulation:** On the Coping Processes Inventory, respondents are provided definitions of various coping behaviors and asked how often they use each approach for dealing with problems concerning school, parents, health and sadness.

**IIIC.4f.2a.5. Self-image:** Body Image subscale from the Sexual Self-concept Inventory consists of eight items that index the youth's evaluation of his/her own physical appearance.

**IIIC.4f.2a.6. Self-esteem:** Rosenberg Self-esteem Scale includes a 5-item general positive self-esteem subscale and a 5-item general negative self-esteem subscale.

**IIIC.4f.2a.7. Impulsivity:** Eysenck Impulsiveness Scale includes 13 items that assess personality traits related to impulsivity and venturesomeness.

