**IIIC.4f.2b.5 Quality Assurance (QA):** Weekly QA data will be collected using the American College of Radiology Phantom Test Guidance Manual. The Functional Biomedical Informatics Research Network QA protocol will be used so that changes in image characteristics over the study period can be monitored and corrected.

**IIIC.4f.2b.6. fMRI Data Processing and Analysis:** Each participant's functional images (rest and task) will be corrected for head motion and co-registered to a common atlas space, then smoothed with a 6 mm kernel. After initial pre-processing, the time series at each voxel will have white matter, cerebrospinal fluid and motion-related signals removed via regression, and will be low-pass filtered at 0.1 Hz to retain low frequencies relevant for connectivity estimation. Head motion can still be a significant confound in fMRI connectivity studies, particularly in children. Hence, we will identify volumes that show large displacement (>0.5mm) or large change in global signal (>0.5%) relative to the preceding volume, and remove them prior to connectivity analysis. [The resulting 3 metrics can be summarized to a single number and then compared between groups or used as covariates.]

For the task-based data, event-related neural responses will be modeled with separate canonical hemodynamic response functions for each of the conditions (e.g. wheel types). For instance, BOLD responses to Risk vs. No-Risk trials will be compared, within/across probabilities and expected values. Group-level analysis will compare the trials during which the participants passed the trials (risk-avoidance) to trials where they bet. For the Go/No-Go task, successful Go trials will be compared to both successful and unsuccessful No-Go (inhibition) trials.

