5	Protecting against dangerous behavior	Understand risk prevalence, overall and for your community; Importance of being an approachable parent	Peer pressure; parents' concerns about peer affiliation	Identify peer pressure; compare risk engagers from non-risk engagers; dealing with temptation; prosocial peer affiliation	Caregivers and youth working together to protect youth from risk behaviors	Develop family plan for handling peer pressure and temptation; share expectations and values about risk and friendship
6	Parental protections that reduce high risk behaviors	Learn how to effectively monitor youth; understand the prevalence of sexual activity in teens; establish expectations about sex	Dealing with sexual and substance use temptations	Identifying and avoiding dangerous situations; connecting temptations, dreams, goals, school and future orientation	Our family plan and pledge for positive youth development	Share expectations, dreams, and hopes; discuss/identify family strengths; establish a family creed of strength, growth and competence

**IIIC.5. Primary Outcome Criteria:** Primary outcome variables include fronto-striatal functional connectivity at rest and while performing the WOF task and youth psychological protective factors (cognitive and emotional self-regulation). Other neural measures/circuits, psychological/social-contextual and behavioral variables (**Appendix 1**) will be used either as supplementary measures or as potential covariates. By sharpening our focus to *a priori* specified neural circuits and psychological measures, we hope to increase statistical power and, in turn, our ability to identify important differences in the responses of these circuits according to youth protective factors.

**IIIC.6. Sample Attrition:** The team has experience with intensive longitudinal studies involving difficult-to-reach samples with retention rates exceeding 90% for short-term follow-up (**IIIC.10a**). Even with a liberal estimate of 20% attrition, we will have 102 participants, which will give us sufficient power to detect medium effects (**IIIC.7e**).

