### IIIC.7. Statistical Methods

**IIIC.7a. Data Management:** Data management will be done via remote electronic data capture (*REDCap*). REDCAP was developed at VUMC to insure data integrity and completeness, including compliance with HIPAA (over 300,000 users). Data will be entered immediately after testing on data entry screens designed to duplicate the data collection forms (ACASI; **IIIC.4f.4**). Reports can be generated to track all contacts with the participants.

**IIIC.7b. Procedures for Handling Missing Data:** Missing data will be accounted for by including "missingness" as a covariate if the proportion of missing data is small, or alternatively using multiple imputation methods if the proportion of missing data is large, e.g. >5%.

**IIIC.7c. Data Reduction:** Each hypothesis will be examined using a primary variable, with supplemental information gained from analysis of other related measures (**see IIIC.5**).

**IIIC.7d. Data Analysis:** Descriptive statistics (e.g. means and standard deviations, frequencies and histograms) will be computed for all variables, along with 95% bootstrap confidence intervals. Significance tests will be two-tailed, with  $p < 0.05$ , controlling for multiple comparisons. Pubertal stage/gonadal hormones, gender and SES will be included as concomitant variables in analyses where they are known to correlate with the outcome. These covariates, while not of primary interest, will reduce residual variance and increase the precision of effect estimates for improved statistical power. Secondary analyses will determine if these covariates significantly affect the outcomes. Behavioral/emotional problem score (CBCL/YSR), lifetime history of substance use and dose of the intervention (number of completed sessions) will serve as additional potential covariates.

**IIIC.7d.1. Hypothesis 1:** PAAS will induce greater functional connectivity changes in the reward-drive and cognitive-control (fronto-striatal) circuitry compared to the wait-list condition. Post-treatment neural connectivity

scores will be regressed on group assignment (PAAS vs. wait-list) as the independent variable and baseline (pre-treatment) neural connectivity score as a covariate. Two separate models will be run for resting-state and task-based fMRI connectivity measures. Other covariates (IIIC.7d) will be included if there are group differences.

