**IIIC.7d.2. Hypothesis 2: PAAS-induced changes in youth self-regulation (cognitive and emotional regulation) at 3 months will be mediated by PAAS' effects on changes in neural circuitry.** A mediation process will be modeled using a sequential process of the associations between specified brain responses and self-regulation. The Wager/Lindquist Mediation Toolbox (IIIC.4f.2b.6) will be deployed. Mediation effects are estimated from the product of the regression coefficient (a) when a mediator of interest (e.g. neural response) is regressed on the intervention and regression coefficient (b) when the outcome criterion (self-regulation at 3 mon.) is regressed on the mediator, controlling for the intervention effect. The standard error of the mediated effect can be calculated in various ways, including the bootstrap method. This method is referred to as the product-of-coefficients approach for testing mediation, and provides an efficient overall test of mediation processes.

**IIIC.7d.3. Exploratory Analyses:** We will examine whether baseline characteristics moderate PAAS' effect (e.g. if reward-drive [BAS] score/ neural connectivity in the fronto-striatal circuit interacts with PAAS) on improvement in self-regulation. We will assess the association of neural changes (local/whole brain) with behavioral and social-contextual variables targeted by PAAS (i.e. risky behaviors and parenting behavior). Other functional connectivity changes (e.g. default-mode, cognitive and salience networks, and the fronto-limbic circuit) will be identified and the association between functional connectivity patterns at rest and during task performance will be evaluated.

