**IIIC.7e. Power Analysis:** Statistical power was estimated with G power 3.1.9.2 software. We used traditional criteria (alpha = .05 two-tailed, power = 80%) to estimate statistical power. [Rather than base power estimates on modest pilot samples, we assessed power by *minimum detectable effect size (MDES)*.] For fMRI studies, Thirion et al. recommend sample sizes of 40 per group for reliable estimates of group differences. Given the multiple variables of interest, we selected larger sample sizes. Randomized subjects will be compared in two conditions using a multiple regression model. With N = 102 participants (after accounting for attrition), a multiple regression would have adequate power to detect an effect size as low as  $r = .31$  ( $R^2 = .10$ ). Cohen considers  $r \sim .10/.30/.50$  to be small/medium/large effect sizes. Power will be sufficient to detect medium effects. Because we will use a repeated measures model with covariates, actual power should be somewhat better. A sample size of  $n = 102$  is also sufficient to detect mediation in an analysis with medium-sized  $\alpha$  and  $\beta$  paths.

**IIIC.8. Timeline:** Table 3 shows the expected timeline of activities for the proposed research.

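### Hypothesis 2: adjustment of path b for residual head motion is optional and assigned to no model, and a between-group comparison of motion cannot protect that path

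*Combined protocol and SAP*

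**What the plan says.** All references are to the combined protocol and SAP.

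- **Preprocessing (IIIC.4f.2b.6).** Functional images are realigned, and motion-related signals are regressed out. The plan then warns: "Head motion can still be a significant confound in fMRI connectivity studies, particularly in children". As its response, it removes volumes with displacement above 0.5 mm or global signal change above 0.5% relative to the preceding volume.
- **Participant-level motion (same section).** "The resulting 3 metrics can be summarized to a single number and then compared between groups or used as covariates". No hypothesis or model is named. The reply on motion artifacts in the resubmission introduction says the same.
- **Hypothesis 2 model (IIIC.7d.2).** For path b, "the outcome criterion (self-regulation at 3 mon.) is regressed on the mediator, controlling for the intervention effect". No other adjustment is given.
- **Covariates (IIIC.7d).** "Pubertal stage/gonadal hormones, gender and SES will be included as concomitant variables in analyses where they are known to correlate with the outcome". The further potential covariates are the CBCL/YSR score, lifetime substance use and number of sessions completed. Motion is in neither list. Under Hypothesis 1 (IIIC.7d.1), other covariates enter only when the groups differ.
- **Phase 1 control (IIIC.1).** The overview says that Aim 2 controls for Phase 1 values. IIIC.7d.2 does not repeat this.
- **Outcome (IIIC.4f.2a).** The seven-measure index includes a self-control inventory that covers "poor self-control (e.g. impulsivity, immediate gratification, distractibility, and low frustration tolerance", and a separate impulsiveness scale.

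**The concern.** Path b is an association within arms. Randomisation protects Hypothesis 1 and path a, but it does not make connectivity independent of other causes of self-regulation. A restless youth plausibly scores worse on impulsivity and distractibility and also moves more in the scanner, which distorts measured connectivity. The trait is then a common cause of the mediator as measured and of the outcome, and scanner motion is its observable marker.

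Motion can be perfectly balanced between PAAS and wait-list while this happens. A between-group comparison would then find nothing, and so would a rule that adds covariates only when groups differ. A significant product a×b could be reported as neural mediation when part or all of path b reflects restlessness. Aim 2 is meant to guide refinement of the program, so such a result would mislead.

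**Working it through.** **Inputs from the plan.** "alpha = .05 two-tailed, power = 80"% (IIIC.7e). 1:1 allocation (IIIC.4f.1). "Even with a liberal estimate of 20% attrition, we will have 102 participants" (IIIC.6), since 128 × 0.8 = 102.4. The stated detectable effect is r = .31 (R² = .10).

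**The plan's own figure.** With λ = N·R²/(1−R²) = 102 × .10/.90 = 11.33, an omnibus F test with three predictors has power .799. At r = .31, λ = 102 × .0961/.9039 = 10.84 and power is .780. The stated figure is therefore reproduced if three predictors were meant (the count is not stated). A single tested coefficient has power .903 at r = .31. This point does not affect the detectable effect.

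**Assumption not in the plan.** Restlessness U has correlation q (absolute) with both connectivity M and self-regulation Y, *after* preprocessing. The plan gives no value; q = .2 to .5 was tried.

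**Model.** M = aX − qU + e₁ and Y = −qU + e₂, with unit variances, U independent of arm X (motion balanced) and true b = 0. If U is left out, path b estimates

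- b* = q²/(1−a²), with partial correlation r* = q²/√(1−a²).

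With a = .31, 1−a² = .9039 and its square root is .9507. The Fisher statistic is atanh(r*) × √(102−4). The chance that both paths are significant is roughly .903 × P(path b significant).

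| q | b* | r* | Fisher statistic | P(path b) | × .903 | Simulated, both paths |
|---|---|---|---|---|---|---|
| .2 | .044 | .042 | 0.42 | .070 | .063 | .062 |
| .3 | .100 | .095 | 0.94 | .156 | .141 | .142 |
| .4 | .177 | .168 | 1.68 | .391 | .353 | .368 |
| .5 | .277 | .263 | 2.67 | .760 | .686 | .696 |

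The simulation used 6,000 trials and the joint-significance test as a stand-in for the bootstrap test of a×b. At q = 0 it gives .041. Separate runs at a = .30 gave about 5-6%, 14% and 34-35% for q = .2, .3 and .4.

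**If a = 0.** Path a is significant in only about 5% of trials, so the joint rate is about .05 × P(path b). Simulated rates are .004, .007, .017 and .035 for q = .2 to .5. If PAAS lowers motion (r = −.2) and has no other effect on connectivity, they are .004, .012 and .046 for q = .2, .3 and .4.

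**If Phase 1 connectivity and Phase 1 self-regulation are in the model** (a about .30, b = 0):

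- Restlessness a fixed trait (share of motion variance .5 to .8, other reliabilities .5): about 5%, 6% and 7% for q = .2, .3 and .4.
- Restlessness shifts between phases and the 3-month outcome follows its week-6 level: from about 6% at q = .2 to 17-18% at q = .4 with stability .8, and from about 7% to 36-37% with stability .5.

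**If motion is added to both models.** The rate is about 4-6% in every setting tried. Power for true a = b = .31 goes from .787 to .784.

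**The case against.** The strongest reply has five parts.

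1. **The plan does handle motion.** It has mock-scan practice, padding, a forehead strap, a break between scans, realignment, motion regression and volume removal, and the quoted sentence allows covariate use. The warning about motion in children introduces volume removal; it does not admit to motion left after that step. This stands. A reader might infer that the plan ignores motion; the documents do not support that. The gap is narrower: adjustment for *residual* motion is optional and assigned to no model.
2. **A confounded path b does not by itself create mediation.** This stands. A reader might infer that restless youth alone can produce a false mediated effect, but path a must also be significant, and with a = 0 the rate stays under 5%. It is limited comfort: a non-zero path a is what Hypothesis 1 predicts, and if that holds, path b is the only barrier left.
3. **IIIC.1 promises control for Phase 1 values.** This stands in part. That control removes most of the bias from a fixed trait but little or none if restlessness shifts between phases, and the operative model in IIIC.7d.2 omits it.
4. **The assumed correlations may be too high.** Youth with clinical-level behavioral or emotional problems are excluded (IIIC.4c), the index also covers self-esteem, body image and future orientation, and CBCL/YSR is a potential covariate. This is fair, and it is why a range is shown.
5. **Motion does not cause self-regulation.** Correct. The trait is the common cause, which is a further reason to include Phase 1 self-regulation.

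**Conclusion.** The point holds in this form: nothing in the plan commits Hypothesis 2 to a participant-level motion covariate, and one of the two options offered, a between-group comparison, cannot protect path b. If PAAS changes connectivity (a about .30) and b = 0, false mediation at N = 102 is about 5-6%, 14% and 35% at assumed residual correlations of .2, .3 and .4.

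These are conditional figures, and the documents give no basis for choosing among them. A reader might take 14% or 35% as the expected error rate of Aim 2. That is not supported: the correlations are assumed, the figures require a non-zero path a, and they describe the IIIC.7d.2 model without the Phase 1 control stated in IIIC.1. With that control, the rates run from about 5-7% to little or no reduction, depending on how stable restlessness is. Adding motion brought the rate to about 4-6% in every setting tried.

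The change should be made before the Hypothesis 2 analysis. The Hypothesis 1 comparison and the stated detectable effect are not undermined.

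**What to change.** In IIIC.7d.2:

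- Define one motion summary per scan, for example mean volume-to-volume displacement or the share of volumes removed.
- Include it in both the mediator and the outcome model, for rest and for task, whether or not the groups differ on motion.
- Include Phase 1 connectivity and Phase 1 self-regulation in the same models, so that IIIC.7d.2 agrees with IIIC.1.
- State that a between-group comparison of motion is descriptive and does not decide whether motion enters Hypothesis 2.
- Report Hypotheses 1 and 2 with and without week-6 motion, because it is measured after randomisation and PAAS may affect it.

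**Cost.** SAP wording, a few degrees of freedom, and a summary derived from data that preprocessing already yields. The simulated loss of power from adding motion is .787 to .784. The one substantive downside is that any part of the mediated effect that runs through PAAS reducing motion is removed; the paired reporting makes this visible.

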**IIIC.4f.2b.3. The WOF Task:** This task allows for the analysis of both risk-seeking and risk-avoidance (Fig 7). During each trial, the participants will be shown a wheel on which the probabilities of winning and losing points are shown as pink and yellow sections, respectively. The number of points that can be won or lost is printed on the wheel sections. The words “Bet” and “Pass” are displayed each time, prompting participants to select one or the other. For the present study, this “decision phase” is the period of interest. After 3 seconds, the wheel spins for a variable, randomly jittered period (1, 3, 5, or 7 sec), and the final result is displayed for 1 sec. If participants choose to bet, and the wheel lands on the pink section, they win the points indicated. Conversely, if the wheel lands on the yellow section they lose the number of points shown. These amounts will be added (or subtracted) to a running total that is not revealed until the end of the task. If participants choose to pass, they still see the outcome but no points will be added or deducted.

Win amounts are kept constant while probability and loss amounts are manipulated orthogonally resulting in 6 different wheels that represent 4 win/loss ratios (100/0, 60/40, 40/60, 0/100) and 2 levels of expected value (EV; +12 and -12). Participants are not explicitly told about the uniformity of expected values. The 0/100 wheel (100% chance of losing 12 points) and the 100/0 wheel (100% chance of winning 12 points) serve as no-risk control conditions and each is presented 8 times. Each 40/60 and 60/40 wheel (EV+ and EV-) is presented 22 times across 4 blocks. Behavioral outcomes include risk-seeking (percent of trials betted), risk-avoidance (percent of trials passed), and response times across conditions of varying probabilities and expected values. We found no practice effects with repeated tasks in at-risk adolescents during longitudinal follow-up ([name], unpublished data).

**IIIC.4f.2b.4. Go/No-Go Task:** The task assesses behavioral responses, with the subjects selectively responding to target stimuli (“X” ~.80 probability) and inhibiting responses to infrequent non-target stimuli (“K”~.20 probability; **IIIC.3d**). The task consists of two runs, with 245 trials per run (7 min) and a random inter-stimulus interval.

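### The pass-versus-bet contrast for the Wheel of Fortune (WOF) task is sorted by the youth's own choices and not separated from wheel value, so a betting change that differs by expected value can pass for a neural one

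*Combined protocol and SAP*

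**What the plan says.** The WOF task (IIIC.4f.2b.3) uses six wheels with "2 levels of expected value (EV; +12 and -12". On the four risky wheels, "Each 40/60 and 60/40 wheel (EV+ and EV-) is presented 22 times across 4 blocks". The 100/0 and 0/100 wheels "serve as no-risk control conditions and each is presented 8 times". On every trial the youth may bet or pass. The same section lists betting itself as an outcome: "Behavioral outcomes include risk-seeking (percent of trials betted), risk-avoidance (percent of trials passed").

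The analysis section (IIIC.4f.2b.6) first describes the task model: "event-related neural responses will be modeled with separate canonical hemodynamic response functions for each of the conditions (e.g. wheel types"). It then offers, as an example, that "BOLD responses to Risk vs. No-Risk trials will be compared, within/across probabilities and expected values". The next sentence gives the comparison it labels group-level: "Group-level analysis will compare the trials during which the participants passed the trials (risk-avoidance) to trials where they bet".

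The primary task outcome (IIIC.5) is "fronto-striatal functional connectivity at rest and while performing the WOF task". IIIC.4f.2b.6 computes task connectivity with the gPPI toolbox but does not name the contrast that enters it. Under IIIC.7d.1 the post-treatment connectivity score is regressed on arm and on the baseline score.

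**The concern.** Bet and pass are behaviours observed after randomisation, not conditions set by the task. The design balances wheels across EV, and sorting trials by choice loses that balance. A youth who attends to value puts mostly EV+ wheels on the bet side and mostly EV- wheels on the pass side. Nothing in the text removes the certain wheels either, so passing on a sure loss could count as risk-avoidance and betting on a sure win as risk-taking.

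A change in betting is foreseeable here. The Introduction (Approach, item 2) ties WOF behaviour to reward-seeking traits and real-life risk behaviour, which PAAS is meant to influence. If PAAS taught youth to decline unfavourable wheels in particular, the wheel mix on each side of the contrast would differ by arm at the post-intervention scan. An arm difference could then reflect which wheels were sorted where. Adjusting for a baseline score cannot remove a mix that changes after baseline.

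**Working it through.** **Inputs from the documents.** Risky trials: 4 × 22 = 88 (44 EV+, 44 EV-). No-risk trials: 2 × 8 = 16 (8 sure wins at +12, 8 sure losses at -12). Total 104, of which 52 are at +12 and 52 at -12. Planned analysis size: 128 × 0.8 = 102.4, that is 102 as stated in IIIC.6, or 51 per arm. The plan gives no figure of its own for this contrast.

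**Assumed, because the documents give no bet rates.** Bet probabilities p+ on EV+ and p- on EV- risky wheels; all sure wins are bet and all sure losses passed.

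**Formula.** Bets on EV+ trials: 44p+ + 8. Bets on EV- trials: 44p-. Let D be the first minus the second, B the total bets, and P = 104 - B the total passes. Mean EV is 12D/B on bet trials and -12D/P on passed trials. The gap is 12D(1/B + 1/P) = 1248D/(BP), with a maximum of 24.

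| p+, p- | B | P | D | Gap |
|---|---|---|---|---|
| 0.80, 0.30 | 56.4 | 47.6 | 30.0 | 13.9 (6.4 vs -7.6) |
| 0.80, 0.15 | 49.8 | 54.2 | 36.6 | 16.9 (8.8 vs -8.1) |
| 0.70, 0.60 | 65.2 | 38.8 | 12.4 | 6.1 |
| 0.90, 0.15 | 54.2 | 49.8 | 41.0 | 19.0 |
| 0.80, 0.40 | 60.8 | 43.2 | 25.6 | 12.16 |
| 0.60, 0.20 | 43.2 | 60.8 | 25.6 | 12.16 |

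Rows 1 and 2: a selective fall in EV- betting raises the gap by 16.923/13.946 - 1 = 21%. Rows 3 and 4 are the ends of the assumed range. Rows 5 and 6: betting falls from 60.8/104 = 58% to 43.2/104 = 42% of trials and the gap does not move. The log-odds shift is the same at both EV levels: ln(4) - ln(1.5) = 0.98 for EV+ and ln(0.667) - ln(0.25) = 0.98 for EV-.

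**Dropping the certain wheels is not enough.** On the 88 risky trials the gap is 1056D/(BP). At (0.8, 0.3), D = 22, B = 48.4 and P = 39.6, so the gap is 12.1. At (0.8, 0.15), D = 28.6, B = 41.8 and P = 46.2, so it is 15.6. Within one EV level every trial has the same EV, so the gap is zero at any bet rate.

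**Effect on a test.** A simulation used 51 per arm, 88 risky trials, 1,000 runs per scenario and a two-sample t-test at 0.05. The response depended on wheel EV only and was the same in both arms. Base bet rates were 0.8 and 0.4. The EV+ versus EV- response difference was 0.5 or 1.0 trial SD.

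| Betting change in one arm (log-odds) | Raw pass/bet rejects | Within-EV rejects |
|---|---|---|
| None | 4.2-4.6% | 5.0% |
| EV- only, -0.5 (40% to 1/(1+e^0.905) = 29%) | 17.9-46.2% | 5.1-5.6% |
| EV- only, -1.0 (40% to 1/(1+e^1.405) = 20%) | 41.9-91.1% | 5.7-6.2% |
| Both levels, -0.5 or -1.0 | 4.9-6.0% | 4.1-6.0% |

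**Sparse cells.** At (0.95, 0.90), passes number 2.2 + 4.4 + 8 = 14.6, of which 8 (55%) are sure losses and 6.6 are risky.

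**The case against.** The strongest reply is that the sentence belongs to a paragraph on event-related BOLD responses, whereas the primary outcome is gPPI connectivity. A reader might infer that Hypothesis 1 and the Hypothesis 2 mediator are therefore biased. The documents do not support that, because nowhere is pass/bet named as the gPPI contrast. What remains is that the contrast is unnamed, and that the one labelled group-level is vulnerable if it is used.

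A reader might also infer that any change in betting shifts the contrast. It does not: bias needs a change that differs by EV and a response that varies with EV, and the documents show neither.

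Nor is pass/bet the only WOF comparison in the plan. Risk versus No-Risk, across and within EV, is in the preceding sentence, and wheel types are the example regressors. But no sentence carries wheel value into the pass/bet comparison.

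Inclusion of the certain wheels is unstated rather than specified, since the text does not say all trials. Exclusion of near-constant bettors would likewise be an inference, because no rule on it is given. IIIC.4f.2b.3 may also mean its betting percentages to be broken down by probability and EV, although the wording leaves that open.

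Finally, Risk versus No-Risk is not a neutral replacement. It rests on 16 no-risk trials and does not isolate choice. If bet and pass decisions evoke different responses, a change in betting still moves its Risk average. That point stands, so the fix does not insist on it.

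**Conclusion.** The point holds in a limited form. As written, pass versus bet confounds choice with wheel value whenever youth bet more on EV+ than EV- wheels. It can show an arm difference without a neural one if PAAS changes betting selectively by EV and the response depends on EV. The sizes rest on assumed bet rates: an EV gap of about 6 to 19 of 24 points, and a 21% rise in the example. EV points describe the stimulus mix, not bias in connectivity. The simulated rejection rates of 18% to 91% likewise depend on the assumed response sizes and on betting falling on EV- wheels only. Whether the primary analysis is exposed cannot be settled from the documents.

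**What to change.** 1. Restrict pass versus bet to the 88 trials on the 40/60 and 60/40 wheels.
2. Estimate it within EV level and pool over the two strata, or put wheel EV in the first-level model. Fix the pooling weights in advance, so that a choice effect that differs by EV does not bring the mix back in.
3. Pre-set a minimum number of bets and of passes, and say how youth below it are handled.
4. Compute percent bet and percent passed on risky wheels.
5. Name the contrast entering gPPI: either this EV-stratified contrast or the task-defined Risk versus No-Risk contrast already in IIIC.4f.2b.6.

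This changes wording and the first-level model and needs no new data. The cost is fewer trials per cell (44 per EV level before splitting by choice), hence some loss of precision and some youth with sparse cells. EV strata still let win probability differ between bet and passed trials. Strata by wheel would remove that too, but with only 22 trials each.
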